Study Protocol: Effectiveness and safety of Bictegravir/emtricitabine/tenofovir alafenamide (B/F/TAF) in HIV-1 infected patients with Active illicit Substance use (BASE)

Investigators: [name], [name], [name], [name], [name], [name]

NCT: 03998176

Hypothesis: People living with HIV (PWH) that use illicit substances receiving B/F/TAF will have virologic suppression similar to PWH that do not use illicit substances receiving B/F/TAF without safety concerns or treatment emergent resistance

Abstract:

Description:

Illicit substance use is a growing concern across the United States and has been linked to HIV outbreaks and viral hepatitis. Close to half of people living with HIV (PWH) struggle with a substance use disorder often leading to non-adherence of antiretroviral therapy (ART) increasing the risk of poor treatment outcomes and potential HIV transmission. Appropriate choice of ART for PWH who use illicit substances is unknown. Boosted protease inhibitor regimens are utilized for their high genetic barrier to resistance, however, concerns for drug-drug interactions with illicit substances are present. The clinical utility of an integrase strand inhibitor (INI) based regimen is unknown. We aim to assess the effectiveness and safety of bictegravir/emtricitabine/tenofovir alafenamide in PWH who actively use illicit substances.

Eligibility:

Eligible participants for the study will be HIV-1 infected patients at the Specialty Care Center with HIV viremia > 1000 copies/mL and ongoing substance use by urine drug screen or self-reported within 6 months. Participants must also have a creatinine clearance of 30 mL/min or greater, no tenofovir or INI HIV resistance mutations, and not be pregnant. Illicit substances will include: methamphetamine, heroin, cocaine, PCP, GHB, ketamine, or inappropriate benzodiazepine, prescription opiate, or prescription stimulant usage.

Interventions/Evaluations:

This is a single-center, single-arm, prospective, pilot study to evaluate the effectiveness and safety of B/F/TAF in PWH and active illicit substance use. We aim to evaluate the proportion of patients at week 24 with undetectable viral loads (<50 copies/mL). We plan to enroll 45 participants.

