 - c. Evaluate the retention in care of PLWH on B/F/TAF with ongoing illicit substance use
 - d. Evaluate the medication adherence of PLWH on B/F/TAF with ongoing illicit substance use

Endpoints:

1. *Primary*

- a. Proportion of participants with ongoing illicit substance use on B/F/TAF with HIV RNA <50 copies/mL at week 24 by FDA Snapshot Algorithm
- 2. *Secondary*
 - a. Proportion of participants who experience adverse events (grade 3 or above) at week 24 and 48
- 3. *Exploratory*
 - a. Proportion of participants with HIV RNA <50 copies/mL at week 48 by FDA Snapshot Algorithm
 - i. Reported as demographics, intention to treat, and per-protocol
 - b. Proportion of participants with HIV RNA <50 copies/mL at week 48 by FDA snapshot algorithm adjusted by type of illicit substance use
 - c. Proportion of participants with treatment emergent resistance at week 24 and 48
 - d. Change in CD4 at week 24 and 48 from baseline
 - e. Proportion of participants completing follow-up visits through weeks 24 and 48
 - i. Calculated as completed study visits/total number of study visits.
 - f. Adherence assessment
 - i. Adherence measure
 - 1. Self-reported adherence questionnaire
 - 2. Pill counts/PDC
 - ii. Tenofovir Pharmacokinetic Sampling
 - 1. TDF-DP and FTC-TP via DBS

Study Design: Prospective, single arm, open-label, pilot study

1. Documented HIV infection
2. ≥ 19 years old
3. Self-reported illicit substance use or confirmed by urine drug screen within past 6 months
 - a. Cocaine
 - b. Heroin
 - c. Methamphetamine
 - d. PCP/ketamine/GHB
 - e. Opiates
 - f. Inappropriate use of prescription pills (opiates/benzodiazepines/stimulants) regardless of prescription
4. HIV RNA $\geq 1,000$ copies/mL not presently taking B/F/TAF

5. Any CD4 count
6. Creatinine clearance >30 mL/min (Cockcroft-Gault)
7. ALT and AST < 5 times the upper limit of normal
8. Willing and able to give written informed consent

Exclusion Criteria:

1. History of INI or TAF-related resistance mutations as defined by the IAS-USA
2. Pregnancy
3. Any concomitant use of dofetilide or known medications to reduce systemic exposure to B/F/TAF (i.e. rifamycins, carbamazepine, St. John's Wort)
4. Serious illness requiring systemic treatment (i.e. prolong intravenous treatment such as chemotherapy, extended antibiotic therapy, etc) and/or hospitalization within 30 days prior to entry

Methods:

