Descriptive summaries will be presented using means, medians, standard deviations, and ranges for continuous variables and frequencies and percentages for categorical variables. Patients achieving HIV RNA <50 copies/mL at week 24 will be presented as a proportion and 95% confidence interval. Counts and percentages will be used to describe safety assessment, retention and adherence of B/F/TAF in HIV infected patients with ongoing illicit substance usage. Adherence will also be evaluated with summary statistics of drug levels measured in patients at the 24 week visit. A logistic regression model may be considered to investigate the effect of adherence on the 24 week outcome.

References

1. Substance Abuse and Mental Health Services Administration (2018). Results from the 2017 National Survey on Drug Use and Health. Rockville, MD: Substance Abuse and Mental Health Services Administration.
2. Centers for Disease Control and Prevention. HIV Surveillance Report, 2017; vol. 29. <http://www.cdc.gov/hiv/library/reports/hiv-surveillance.html>. Published November 2018. Accessed [December 2018].
3. Peters, P.J., et al., *HIV Infection Linked to Injection Use of Oxymorphone in Indiana, 2014-2015*. N Engl J Med, 2016. **375**(3): p. 229-39.
4. Hartzler, B., et al., *Prevalence and Predictors of Substance Use Disorders Among HIV Care Enrollees in the United States*. AIDS Behav, 2017. **21**(4): p. 1138-1148.
5. Meyer, J.P., A.L. Althoff, and F.L. Altice, *Optimizing care for HIV-infected people who use drugs: evidence-based approaches to overcoming healthcare disparities*. Clin Infect Dis, 2013. **57**(9): p. 1309-17.
6. Kamarulzaman, A. and F.L. Altice, *Challenges in managing HIV in people who use drugs*. Curr Opin Infect Dis, 2015. **28**(1): p. 10-6.
7. Shubber, Z., et al., *Patient-Reported Barriers to Adherence to Antiretroviral Therapy: A Systematic Review and Meta-Analysis*. PLoS Med, 2016. **13**(11): p. e1002183.
8. Panel on Antiretroviral Guidelines for Adults and Adolescents. Guidelines for the Use of Antiretroviral Agents in Adults and Adolescents Living with HIV. Department of Health and Human Services. Available at

<http://aidsinfo.nih.gov/contentfiles/lvguidelines/AdultandAdolescentGL.pdf>. Section “What To Start.” [December 2018]. [F-1 – F-42]

9. Dierynck, I., et al., *Binding kinetics of darunavir to human immunodeficiency virus type 1 protease explain the potent antiviral activity and high genetic barrier*. J Virol, 2007. **81**(24): p. 13845-51.

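### The hypothesis claims absence of safety concerns and emergent resistance, but neither outcome gets a confidence interval, and a zero or small count in at most 45 people cannot support absence

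*Combined protocol and SAP*

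**What the plan says.** The Hypothesis paragraph predicts suppression similar to that in people who do not use illicit substances, "without safety concerns or treatment emergent resistance". It sets no tolerable rate for either outcome.

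Under Endpoints, the only secondary endpoint is the proportion with a grade 3 or higher adverse event at weeks 24 and 48. Resistance is exploratory: "Proportion of participants with treatment emergent resistance at week 24 and 48".

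The Data analysis section treats the outcomes differently:

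- Primary endpoint: "Patients achieving HIV RNA <50 copies/mL at week 24 will be presented as a proportion and 95% confidence interval".
- Safety: "Counts and percentages will be used to describe safety assessment, retention and adherence of B/F/TAF".
- Resistance is not named. The only text that reaches it is the general rule of "frequencies and percentages for categorical variables".

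The precision table under Sample Size Justification covers the primary proportion only. The study is described as "Prospective, single arm, open-label, pilot study", and the Abstract says "We plan to enroll 45 participants".

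Under Virologic Failure, genotyping follows confirmed failure only: HIV RNA above 400 copies/mL after week 12, confirmed by a repeat within 28 days.

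**The concern.** A hypothesis of absence that carries no criterion leaves the observed percentage as the only thing to judge it by. At this sample size that percentage is weak evidence. A result of 0 (0%) is what one would hope to see if the regimen were free of emergent resistance, but it is also compatible with a risk of several percent. A count and percentage alone do not put that in front of the reader; an upper confidence limit does.

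At stake is the concluding statement on two of the three parts of the hypothesis, in a population that the Brief Description says is typically excluded from trials. No primary result is affected.

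**Working it through.** **Inputs.** Planned enrolment is 45 (Abstract). The number targeted after attrition is 30, and attrition is put at about 50% (Sample Size Justification). Intervals are two-sided at 95% (same section). The documents give no expected rate of resistance or of grade 3 or higher events, so the 2% and 5% used below are illustrative assumptions.

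**1. The plan's own figure.** For 30 participants and a proportion of 0.70, the plan states 0.51 to 0.85, width 0.35. The exact (Clopper-Pearson) interval for 21/30 is 0.506 to 0.853, width 0.347, which matches. All 15 rows of the table reproduce to rounding by this method. In the same row Wilson gives a width of 0.312, Wald 0.328 and continuity-corrected Wald 0.361, none of which matches. The plan has therefore already used exact intervals for a single proportion.

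**2. Denominators.** Three are shown:

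- 45: everyone enrolled and treated.
- 30: the plan's target after attrition.
- 22: what remains if 50% of 45 are lost (45 × 0.5 = 22.5, rounded down).

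The last is a pessimistic reading of the plan's attrition figure. For adverse events the natural denominator is all treated participants, because events are assessed at every visit.

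**3. What a zero count excludes.** The exact two-sided 95% upper limit for 0/n is 1 − 0.025^(1/n). The chance of seeing no event at true risk p is (1 − p)^n.

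| n | Upper limit for 0/n | P(no event), p = 2% | P(no event), p = 5% |
|---|---|---|---|
| 45 | 7.9% | 0.98^45 = 40% | 0.95^45 = 10% |
| 30 | 11.6% | 0.98^30 = 55% | 0.95^30 = 21% |
| 22 | 15.4% | 0.98^22 = 64% | 0.95^22 = 32% |

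At an assumed 5%, a zero count is the less common result at every n, but it is far from rare with 22 or 30 people. At 2% it is about as likely as not with 30, and more likely than not with 22.

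**4. Adverse events.** Here a zero count is less likely and the question is precision. As an illustration, 3/45 = 6.7% has an exact 95% interval of 1.4% to 18.3%.

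**5. Who can be counted as resistant.** After week 12, scheduled HIV RNA is measured only at weeks 24 and 48 (Study Follow-up/Labs table). A participant lost before then, or viremic without a confirmatory repeat, is not genotyped under the Virologic Failure section. Addendum A has an emergent resistance field at weeks 6, 24 and 48, but nothing there says that everyone is genotyped. The resistance denominator is not defined. Using everyone treated counts untested people as free of resistance. Using only those genotyped gives a small n: if five were tested (an assumption), 0/5 has an exact upper limit of 52%.

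**The case against.** The strongest reply is that this is a single-arm pilot in which safety is secondary and resistance exploratory, the objectives are to evaluate these outcomes, and counts with percentages are a normal descriptive choice. A reader given the count and the denominator can compute the exact limit. The protocol also provides for a monitoring committee to review safety at two time points. All of this is true, and it keeps the point modest. It does not remove the mismatch between an absence clause in the hypothesis and an analysis that gives no bound. The plan justified its sample size by interval precision, so the same method for two more proportions is in keeping with its own approach.

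A reader might infer that the investigators will present a zero count as proof of absence. The documents do not say so: there is no success criterion, test or interpretation rule for either outcome. The reading is only left open by the wording of the hypothesis.

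A reader might also take the hypothesis to predict no grade 3 or higher events at all. It speaks of safety concerns, which is not the same thing. With no comparator and no tolerable rate, an interval shows how imprecise the estimate is; it does not settle whether a concern exists.

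Finally, the safety sentence does not mention resistance. That half of the point rests on the general rule for categorical variables and on the lack of any interval for resistance elsewhere.

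**Conclusion.** The point holds as a cheap improvement to the analysis and reporting of secondary and exploratory endpoints. The hypothesis asserts absence, the only planned interval is for week 24 suppression, and a zero count would leave a true risk of up to 7.9% (n = 45), 11.6% (n = 30) or 15.4% (n = 22) not excluded. These limits rest on the exact two-sided 95% method and on the denominators set out above; the chances of a zero count rest in addition on the assumed 2% and 5% risks.

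The zero-count argument applies mainly to resistance. The limits on the all-treated denominator are optimistic there if some viremic participants are never genotyped. For grade 3 or higher events the finding is imprecision only. The documents do not support saying that a zero count is likely whatever the true risk, or that a false claim of safety is planned.

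**What to change.** **Data analysis.** Add that grade 3 or higher adverse events and treatment-emergent resistance, each at weeks 24 and 48, will be reported as counts, percentages and exact (Clopper-Pearson) 95% confidence intervals. Name resistance explicitly, since the present safety sentence does not cover it. Use all treated participants as the safety denominator.

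**Resistance denominators.** Report resistance on two: all treated participants, and those actually genotyped after confirmed virologic failure. Beside them, give the number with HIV RNA above the failure threshold who were not genotyped. A denominator of participants with an HIV RNA result would not serve, because it counts viremic people without a genotype as free of resistance.

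**Hypothesis.** Reword the safety and resistance clause as estimation: the study will estimate the proportion with each outcome and its 95% confidence interval. Do not write in a bound taken from the observed data, since a hypothesis framed that way is always met.

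**Cost.** A few sentences in the protocol and a few lines of output, with no change to sample size, visits or data collection. The statement on resistance and safety becomes less favourable: with no cases among 45, it would say that a risk of up to 7.9% is not excluded.

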Race	X					
Ethnicity	X					
Education	X					
Gender	X					
ART Exp	X					
Housing	X					
Income	X					
Reported Illicit Substance or UDS Result	X					
Baseline/Archived Resistance	X					
Clinical Information						
CBC	X			X		X
Creatinine	X	X		X		X
AST	X	X		X		X
ALT	X	X		X		X
HBV c Ab	X					
HBV s Ab	X					
HBV s Ag	X					
HCV Ab	X					
HIV RNA	X	X		X		X
CD4	X			X		X
CD4%	X			X		X
CD4/CD8	X			X		X
Pregnancy (if applicable)	X	X	X	X	X	X
Emergent Resistance		X		X		X
Safety/AE Assessment						
Physical Exam						
	X			X		X

Questionnaire						
ACTG Adherence		X	X	X	X	X
NIDA ASSIST	X		X	X	X	X
SF-12 Survey	X			X		X
Lab Collection						
DBS Card Collection		X		X		X

Addendum B: Adherence Questionnaire – adapted from ACTG Visual Analog Scale

BASE Study: ACTG Adherence

Name:

Visit Week:

DOB:

Participant ID:

Reported Adherence

[figure not shown]
We understand that many people on anti-HIV medications find it very difficult to take them regularly. We would like to know HOW MUCH of your anti-HIV medications you have taken DURING THE LAST MONTH.

Please put a cross (**X**) on the line below at the point showing your best guess about how much of your anti-HIV medication you have taken **in the last month**. We would be surprised if this was 100% for most people.

For example: **0%** means you have taken **none** of your anti-HIV medication.

50% means you have taken **half** your anti-HIV medication.

100% means that you have taken **every single dose** of your anti-HIV medication in the past month.

Self-reported adherence score: _____

Addendum C: Substance Use Questionnaire – adapted from NIDA-ASSIST

BASE Study: NIDA ASSIST

Name: _____ Visit Week: _____
DOB: _____ Participant ID: _____

NIDA Quick Screen:

In the past year, how often have you used the following?

Alcohol	Never	Once or twice	Monthly	Weekly	Daily or Almost Daily
• Men (≥ 5 drinks/day)					
• Women (≥ 4 drinks/day)					
Tobacco Products					
Prescription Drugs for Non-Medical Reasons					
Illegal Drugs					

NIDA Modified Screen:

1. In your lifetime, which of the following substances have you ever used?

Cannabis (marijuana, pot, grass, hash, CBD, etc.)	Yes	No
Cocaine (coke, crack, etc.)		
Prescription stimulants (Ritalin, Concerta, Dexedrine, Adderall, diet pills, etc)		
Methamphetamine (speed, crystal meth, Tina, ice, etc)		
Inhalants (nitrous oxide, glue, gas, paint thinner, "poppers", etc.)		
Sedatives or sleeping pills (Valium, Ativan, Xanax, Librium, Rohypnol, GHB, etc)		
Hallucinogens (LSD, acid, mushrooms, PCP, Special K, ecstasy, etc)		
Street opioids (heroin, opium, etc)		
Prescription opioids (fentanyl, oxycodone [Oxycontin, Percocet], methadone, Buprenorphine, oxymorphone, hydrocodone [Vicodin])		
Other – specify:		

2. In the past 3 months, how often have you used the substances you mentioned (first drug, second drug, etc)?

Frequency (Points listed in box)	Never	Once/Twice	Monthly	Weekly	Daily or Almost Daily
Cannabis (marijuana, pot, grass, hash, CBD, etc.)	0	2	3	4	6
Cocaine (coke, crack, etc.)	0	2	3	4	6
Prescription stimulants (Ritalin, Concerta, Dexedrine, Adderall, diet pills, etc)	0	2	3	4	6
Methamphetamine (speed, crystal meth, Tina, ice, etc)	0	2	3	4	6
Inhalants (nitrous oxide, glue, gas, paint thinner, "poppers", etc.)	0	2	3	4	6
Sedatives or sleeping pills (Valium, Ativan, Xanax, Librium, Rohypnol, GHB, etc)	0	2	3	4	6
Hallucinogens (LSD, acid, mushrooms, PCP, Special K, ecstasy, etc)	0	2	3	4	6
Street opioids (heroin, opium, etc)	0	2	3	4	6
Prescription opioids (fentanyl, oxycodone [Oxycontin, Percocet], methadone, Buprenorphine, oxymorphone, hydrocodone [Vicodin])	0	2	3	4	6
Other – specify:	0	2	3	4	6

3. In the past 3 months, how often have you a strong desire or urge to use (first drug, second drug, etc)?

Frequency (Points listed in box)	Never	Once/Twice	Monthly	Weekly	Daily or Almost Daily
Cannabis (marijuana, pot, grass, hash, CBD, etc.)	0	3	4	5	6
Cocaine (coke, crack, etc.)	0	3	4	5	6
Prescription stimulants (Ritalin, Concerta, Dexedrine, Adderall, diet pills, etc)	0	3	4	5	6
Methamphetamine (speed, crystal meth, Tina, ice, etc)	0	3	4	5	6
Inhalants (nitrous oxide, glue, gas, paint thinner, "poppers", etc.)	0	3	4	5	6

Sedatives or sleeping pills (Valium, Ativan, Xanax, Librium, Rohypnol, GHB, etc)	0	3	4	5	6
Hallucinogens (LSD, acid, mushrooms, PCP, Special K, ecstasy, etc)	0	3	4	5	6
Street opioids (heroin, opium, etc)	0	3	4	5	6
Prescription opioids (fentanyl, oxycodone [Oxycontin, Percocet], methadone, Buprenorphine, oxymorphone, hydrocodone [Vicodin])	0	3	4	5	6
Other – specify:	0	3	4	5	6

4. In the past 3 months, how often has your use (first drug, second drug, etc) lead to health, social, legal or financial problems?

Frequency (Points listed in box)	Never	Once/Twice	Monthly	Weekly	Daily or Almost Daily
Cannabis (marijuana, pot, grass, hash, CBD, etc.)	0	4	5	6	7
Cocaine (coke, crack, etc.)	0	4	5	6	7
Prescription stimulants (Ritalin, Concerta, Dexedrine, Adderall, diet pills, etc)	0	4	5	6	7
Methamphetamine (speed, crystal meth, Tina, ice, etc)	0	4	5	6	7
Inhalants (nitrous oxide, glue, gas, paint thinner, “poppers”, etc.)	0	4	5	6	7
Sedatives or sleeping pills (Valium, Ativan, Xanax, Librium, Rohypnol, GHB, etc)	0	4	5	6	7
Hallucinogens (LSD, acid, mushrooms, PCP, Special K, ecstasy, etc)	0	4	5	6	7
Street opioids (heroin, opium, etc)	0	4	5	6	7
Prescription opioids (fentanyl, oxycodone [Oxycontin, Percocet], methadone, Buprenorphine, oxymorphone, hydrocodone [Vicodin])	0	4	5	6	7
Other – specify:	0	4	5	6	7

5. In the past 3 months, how often have you failed to do what was normal expected of you because of your use (first drug, second drug, etc)?

Frequency (Points listed in box)	Never	Once/Twice	Monthly	Weekly	Daily or Almost Daily
Cannabis (marijuana, pot, grass, hash, CBD, etc.)	0	5	6	7	8
Cocaine (coke, crack, etc.)	0	5	6	7	8
Prescription stimulants (Ritalin, Concerta, Dexedrine, Adderall, diet pills, etc)	0	5	6	7	8
Methamphetamine (speed, crystal meth, Tina, ice, etc)	0	5	6	7	8
Inhalants (nitrous oxide, glue, gas, paint thinner, "poppers", etc.)	0	5	6	7	8
Sedatives or sleeping pills (Valium, Ativan, Xanax, Librium, Rohypnol, GHB, etc)	0	5	6	7	8
Hallucinogens (LSD, acid, mushrooms, PCP, Special K, ecstasy, etc)	0	5	6	7	8
Street opioids (heroin, opium, etc)	0	5	6	7	8
Prescription opioids (fentanyl, oxycodone [Oxycontin, Percocet], methadone, Buprenorphine, oxymorphone, hydrocodone [Vicodin])	0	5	6	7	8
Other – specify:	0	5	6	7	8

6. Has a friend or relative or anyone else ever expressed concern about your use (first drug, second drug, etc)?

Frequency (Points listed in box)	No, never	Yes, but not in the past 3 months	Yes, in the past 3 months
Cannabis (marijuana, pot, grass, hash, CBD, etc.)	0	3	6
Cocaine (coke, crack, etc.)	0	3	6

Prescription stimulants (Ritalin, Concerta, Dexedrine, Adderall, diet pills, etc)	0	3	6
Methamphetamine (speed, crystal meth, Tina, ice, etc)	0	3	6
Inhalants (nitrous oxide, glue, gas, paint thinner, "poppers", etc.)	0	3	6
Sedatives or sleeping pills (Valium, Ativan, Xanax, Librium, Rohypnol, GHB, etc)	0	3	6
Hallucinogens (LSD, acid, mushrooms, PCP, Special K, ecstasy, etc)	0	3	6
Street opioids (heroin, opium, etc)	0	3	6
Prescription opioids (fentanyl, oxycodone [Oxycontin, Percocet], methadone, Buprenorphine, oxymorphone, hydrocodone [Vicodin])	0	3	6
Other – specify:	0	3	6

7. Have you ever tried and failed to control, cut down or stop using (first drug, second drug, etc)?

Frequency (Points listed in box)	No, never	Yes, but not in the past 3 months	Yes, in the past 3 months
Cannabis (marijuana, pot, grass, hash, CBD, etc.)	0	3	6
Cocaine (coke, crack, etc.)	0	3	6
Prescription stimulants (Ritalin, Concerta, Dexedrine, Adderall, diet pills, etc)	0	3	6
Methamphetamine (speed, crystal meth, Tina, ice, etc)	0	3	6
Inhalants (nitrous oxide, glue, gas, paint thinner, "poppers", etc.)	0	3	6
Sedatives or sleeping pills (Valium, Ativan, Xanax, Librium, Rohypnol, GHB, etc)	0	3	6
Hallucinogens (LSD, acid, mushrooms, PCP, Special K, ecstasy, etc)	0	3	6
Street opioids (heroin, opium, etc)	0	3	6
Prescription opioids (fentanyl, oxycodone [Oxycontin, Percocet], methadone, Buprenorphine, oxymorphone, hydrocodone [Vicodin])	0	3	6
Other – specify:	0	3	6

8. Have you ever used any drug by injection (non-medical use only)?

- No, never
- Yes, but no in the past 3 months
- Yes, in the past 3 months

9. Substance use grading

Substance Involvement Score	Total (SI Score)	Risk Level
Cannabis (marijuana, pot, grass, hash, CBD, etc.)		
Cocaine (coke, crack, etc.)		
Prescription stimulants (Ritalin, Concerta, Dexedrine, Adderall, diet pills, etc)		
Methamphetamine (speed, crystal meth, Tina, ice, etc)		
Inhalants (nitrous oxide, glue, gas, paint thinner, "poppers", etc.)		
Sedatives or sleeping pills (Valium, Ativan, Xanax, Librium, Rohypnol, GHB, etc)		
Hallucinogens (LSD, acid, mushrooms, PCP, Special K, ecstasy, etc)		
Street opioids (heroin, opium, etc)		
Prescription opioids (fentanyl, oxycodone [Oxycontin, Percocet], methadone, Buprenorphine, oxymorphone, hydrocodone [Vicodin])		
Other – specify:		

SI risk Level

Level of risk associate with SI score for Illicit or nonmedical prescription drug use	
0-3	Lower Risk
4-26	Moderate Risk
27+	High Risk

Addendum D: Patient Reported Outcomes – adapted from SF-12

BASE Study: SF-12

Name:

Visit Week:

DOB:

Participant ID:

1. In general would you say your health is:
 Excellent
 Very good
 Good
 Fair
 Poor
2. The following questions are about activities you might do during a typical day. Does your health now limit you in these activities? If so, how much?

Moderate activities, such as moving a table, pushing a vacuum cleaner, bowling, or playing golf:

Yes, limited a lot
 Yes, limited a little
 No, not limited at all

Climbing several flights of stairs:

Yes, limited a lot
 Yes, limited a little
 No, not limited at all

3. During the past week, have you had any of the following problems with your work or other regular daily activities as a result of your physical health?

Accomplished less than you would like:

Yes
 No

Were limited in the kind of work or other activities:

Yes
 No

4. During the past week, have you had any of the following problems with your work or other regular daily activities as a result of your emotional health problems (such as feeling depressed or anxious)?

Accomplished less than you would like:

- Yes
- No

Didn't do work or other activities as carefully as usual:

- Yes
- No

5. During the past week, how much did pain interfere with your normal work (including both work outside the home and housework)?

- Not at all
- A little bit
- Moderately
- Quite a bit
- Extremely

6. These questions are about how you feel and how things have been with you during the past week. For each question, please give the one answer that comes closest to the way you have been feeling. How much of the time during the past week:

Have you felt calm and peaceful:

- All the time
- Most of the time
- A good bit of the time
- Some of the time
- A little of the time
- None of the time

Did you have a lot of energy:

- All the time
- Most of the time
- A good bit of the time
- Some of the time
- A little of the time

None of the time

Have you felt downhearted and blue:

All the time
 Most of the time
 A good bit of the time
 Some of the time
 A little of the time
 None of the time

7. During the past week, how much of the time has your physical health or emotional problems interfered with your social activities (like visiting with friends, relatives, etc.)?

All the time
 Most of the time
 A good bit of the time
 Some of the time
 A little of the time
 None of the time

PCS-12 (Physical Score): _____

MCS-12 (Mental Score): _____

Scoring available at: <http://orthotoolkit.com/sf-12/>

Addendum E: Qualitative Sub-Study

Study Protocol: Engagement in HIV Care and On-going Substance Use: A Qualitative Sub-Study of Perspectives from BASE Study Participants

Investigators: [name], [name], [name], [name]

Objectives:

We aim to qualitatively examine BASE study participants for their experiences and perspectives of BASE study participation impact on engagement in HIV care, treatment adherence, and ongoing substance/mental health.

Brief Description:

Illicit substance use in the United States is a growing concern across all states. Use of illicit drugs such as cocaine, heroin, methamphetamine, prescription opioids and stimulants, and 3,4-methylenedioxymethamphetamine (Ecstasy, MDMA) among others, has remained steady in many parts of the United States¹. Of the 1.2 million PWH in the US, an estimated 48% struggles with a substance use disorder². Poor antiretroviral treatment (ART) adherence and inconsistencies in retention in HIV care has been reported among PWH that use illicit drugs³⁻⁵. Gaps in ART coverage and lack of retention to HIV care are factors that complicate successfully managing PWH who use illicit drugs, often leading to poor treatment outcomes and increased HIV transmission⁶⁻⁸.

The BASE study is a single-arm, pilot study assessing the efficacy and safety of bictegravir/emtricitabine/tenofovir alafenamide, B/F/TAF) over a total of 48 weeks (NCT03998176). At present, roughly 40% of the allotted 45 patients have given consent for BASE study participation with the initial participant's now reaching week 24. Historically, approximately half of the currently enrolled BASE participants have remained out of HIV care and struggled with adherence and ongoing substance use. The study team have been surprised to observe that many of these participants are more engaged in care and not missing study visits. Further, the same participants have reportedly remained adherent to antiretroviral therapy for the first time in years, and some have reduced or ceased their substance use since study enrollment.

In order to examine the underlying reasons for this behavior change, we propose a qualitative study in the form of in-depth, face-to-face interviews with BASE study participants to evaluate the impact of BASE study participation on their treatment adherence, motivations for engagement in HIV care, on-going substance use, mental health, stigma, and access to the necessary support systems.

Hypothesis:

BASE study participation positively impacted the participant's treatment adherence, motivations for engagement in care for HIV, substance use disorders, and mental health.

Objectives:

1. Primary: Determine BASE participant perspectives on how study participation impacted their engagement in HIV care and treatment adherence.
2. Secondary: Determine BASE participant perspectives on how study participation impacted their on-going substance use, mental health, and access to necessary support systems.

Study Design:**Overview**

This study will be a prospective qualitative study design with interest in examining patient perspectives on the impact of BASE study participation on the following topical domains: treatment adherence, motivations for engagement in HIV care, on-going substance use, mental health, stigma, and access to the necessary support systems. We plan to use a semi-structured, in-depth face-to-face interview to evaluate the topical domains previously listed among participants enrolled in the Phase IV trial in the United States (Effectiveness and safety of Bictegravir/emtricitabine/tenofovir alafenamide (B/F/TAF) in HIV-1 infected patients with Active illicit Substance use [BASE]; NCT 03998176). The anticipated timeframe for in-depth interviews is near the BASE week 48 visit window (42 to 60 weeks).

Sample Size/Justification

A sample size of 10 to 15 participants is typically understood to be a sufficient amount to develop themes within a given group. However, we aim to sample roughly half of the BASE participants (20-25) or until thematic saturation is achieved.

Participants:**Inclusion Criteria**

This study will include participants currently enrolled in the BASE study at the Specialty Care Center in Omaha, NE. We will attempt to balance the enrollment by gender and sociodemographic diversity. A summary of BASE inclusion criteria is below:

9. Inclusion Criteria
 - a. Current participant in the BASE study
 - b. Willing and able to give written informed consent (not severely experiencing psychiatric condition or severely under the influence of illicit substances compromising ability to understand and provide consent)
 - c. English speaking

Exclusion Criteria

1. None

Study Procedures**Recruitment**

Research providers (primary investigator or study team provider) who have already had contact with the participants through the BASE study conduct will identify and directly contact potential study participants during a BASE study visit. If the participant is interested in participating in the qualitative

sub-study, study description and obtaining consent would take place in-person at the Specialty Care Center with a subsequent qualitative study visit scheduled in the future.

All study interactions with potential or enrolled participants will be conducted in a private room at the Specialty Care Center.

Consent Process

Written informed consent will be obtained for all participants wishing to enroll in the qualitative sub-study. Written informed consenting will be conducted by research providers (primary investigator or study team provider) prior to any interviewing procedures. All consenting will take place at the Specialty Care Center in a private room. All consenting study team members are CITI trained and the consenting study team member will sign off on the consent.

Study Implementation

After consent has been given, each sub-study participant will be interviewed using a semi-structured, in-depth interview guide. The interview guide (Appendix A) contains a listing of open-ended questions with subsequent sub-question probes to elicit participant experiences and perspectives regarding each core topic.

Topics to be explored within the in-depth interviews include:

1. Living with HIV
2. Living with a substance use disorder
3. Engagement in HIV care
4. Views and experiences with study participation

All in-depth interviews will be conducted by a trained interviewer in qualitative research. Interviews will be conducted in English. All interviews will be audio-recorded and transcribed by study team members for data analysis.

Only one in-depth interview will be conducted for each participant. We expect the interviews to be 1 to 2 hours in length. All interviews will take place in a private room. Since participants are enrolled in the BASE study in a rolling fashion, each participant may hit the week 48 study visit window at different time points. Thus, we expect the timeframe for qualitative interviews to take up to 6 months to allow for at least half of BASE participants reaching week 48.

Interview transcripts will be coded through a qualitative software, QSR NVivo. Within each topic of interest, a thematic analysis approach will be utilized toward the coded transcripts. The study team will examine the emerging themes from the data analysis.

All study data including participant contact information will be collected and stored on University of Nebraska Medical Center (UNMC), secure-servers with password-protected files. All interview forms, audio-records, and transcripts will be identified only by the participants BASE patient identification number.

Data Management and Security

Version 5; Last Update 9/22/22

Data Storage

All data collection forms will be coded with the participants BASE study identification number. Patient identification numbers are stored securely on a UNMC, secure-server and also within REDCap hosted by UNMC. All study records will be stored on a UNMC, secure-server until publication.

Confidentiality

All participants are provided a National Institutes of Health, Certificate of Confidentiality (CoC), for their participation within the BASE study. The CoC has already been applied for and approved prior to BASE study initiation.

Study Risks

Participants within this qualitative study may potentially become embarrassed, frustrated, or uncomfortable with the sensitive questions asked of them during in-depth interviewing regarding their HIV diagnosis, on-going substance use, stigma, etc. Those experiencing psychological distress will be offered a referral for counseling or psychiatric evaluation, including in the emergency room if needed.

Study Benefits

There are no direct benefits to the participants. Possible societal benefits involve informing medical providers on engaging patients with on-going substance use disorders and HIV infection.

Participant Compensation

Participants will be reimbursed with Visa cash cards at a rate of \$20/hour.

Study Management

The primary investigator will oversee all aspects of the study including obtaining informed consent, data collection, and analysis. The study team will identify 1 to 2 doctoral or post-doctoral students to assist in the study conduct. All planned interviews and data analysis will be conducted by the University of Nebraska Omaha (UNO), School of Health and Kinesiology faculty or staff under the guidance of [name]. All interviewers will have CITI certifications and training in qualitative research.

References

1. Substance Abuse and Mental Health Services Administration (2018). Results from the 2017 National Survey on Drug Use and Health. Rockville, MD: Substance Abuse and Mental Health Services Administration.

